2.1 Objectives and related endpoints

Table 2-1 Objectives and related endpoints

Objective(s)	Endpoint(s)

Primary Objective(s)
 
 To characterize hepatic safety aspects of single- and multiple ascending doses of KAE609 in adult malaria patients 	
Endpoint(s) for primary objective(s)
 
 At least 2 CTCAE grades increase from baseline in ALT or AST during the 4 week study period

Secondary Objective(s)
	
Endpoint(s) for secondary objective(s)

Objective(s)	Endpoint(s)

 To evaluate overall safety and tolerability of KAE609. 	
 Standard safety/tolerability assessments (AE incidence and severity, vital signs, ECG, laboratory abnormalities)

 To assess key PK parameters following treatment with KAE609. 	
 PK parameters such as AUC, Cmax, Tmax, T½ etc.

 To assess the efficacy of KAE609 in patients with uncomplicated falciparum malaria. 	
 PCR-Uncorrected adequate clinical and parasitological response (ACPR) and PCR-Corrected ACPR at Days 15 and 29 (i.e., 14 and 28 days post-dose) Parasite and Fever Clearance Times (PCT and FCT) before rescue medication is given

 To assess recrudescence after single and multiple doses of KAE609 	
 Incidence rate of recrudescence at Day 29

3 Investigational plan

3.1 Study design

This will be a multicenter, open label, randomized, dose escalation study to evaluate the hepatic safety and tolerability of KAE609 in adult patients (≥ 18 years and ≥ 45 kg bodyweight) with uncomplicated malaria caused by *P. falciparum*.

Starting dose of KAE609 will be a single dose of 10 mg and following acceptable safety results in the 10 mg treatment arm, the dose of KAE609 will be increased stepwise up to a single dose of 225 mg and multiple doses of 50 mg (QD x3 days) according to schedule below (Figure 3-1).

Based on the safety pattern observed in previous studies with KAE609, LFT parameters, if they rise, are expected to peak within 14 days of treatment. Hence, the decision to escalate to next cohort with higher doses will be based on the criteria as specified in the table below (Table 3-1):

Table 3-1 Decision criteria for dose escalation based on LFT results with KAE609

LFT parameter	Baseline	Maximum post baseline value	Decision to escalate to next cohort
ALT/AST	Within ULN	< 2 times ULN (from Day 1 to Day 15)	Escalate to next cohort after notification to safety review committee, after all the patients in the cohort have been followed for at least 14 days post treatment (study Day 15).
	> 1 to ≤ 1.5 ULN	< 2 times baseline (from Day 1 to Day 15)	
ALT/AST	Within ULN	≥ 2 to < 3 times ULN (from Day 1 to Day 15)	Escalate to next cohort based on review of liver safety (and any other relevant data) by safety review committee, after all the patients in the cohort have been followed for at least 28 days post treatment (Study Day 29)
	> 1 to ≤ 1.5 ULN	≥ 2 to < 3 times baseline (from Day 1 to Day 15)	
ALT/AST	Any baseline value	≥ 2 Grade (CTCAE grades) increase from baseline (at any time point during the study) in: 
 - 2 patients in a 10 patient cohort (Cohorts 1 and 2) or - 3 patients in a 20 patient cohort (Cohorts 3, 4, 5 and 6) 	Suspend recruitment and initiate review of liver safety (and any other relevant data) by safety review committee. Any further progression of the study is based on the decision by the safety review committee.

[figure not shown]
In consultation with the safety review committee, Novartis can suspend recruitment and trigger safety review any time based on safety signals including any potential Hy's law case.

Based on the pre-specified criteria (Table 3-1) and the review of the liver safety data by a safety review committee, the recruitment in Cohort 5 may be stopped and a lower dose of KAE609 i.e. 110 mg may be selected for Cohort 6.

The study could be stopped after Cohort 5 if there is no added advantage for dosing the patients with 225 mg single dose from the perspective of future clinical development of KAE609 and its subsequent use in clinical practice.

Figure 3-1 Study KAE609A2202 diagram

Given the expected sub-therapeutic efficacy of the doses of KAE609 in the first 2 cohorts, a smaller number (N=10) of patients will be included (10 mg Single Dose (SD), 25 mg SD and 10 mg 3 Days) to detect potential LFT increases. In the subsequent cohorts a higher number (N=20) of patients will be included. All patients will be followed up for 4 weeks with close monitoring in an inpatient setting for at least the first 3 days (Study Day 4) for efficacy and safety followed by outpatient monitoring up to Study Day 29.

Patients will remain in the hospital under close supervision until they are discharged by the investigator or designee on Study Day 4. To be discharged, patients should present 2 consecutive study assessments with negative blood smear for *P. falciparum* parasites and clearance of fever. At the discretion of the investigator, patients may remain in hospital for additional days if needed.

Coartem® (Artemether-Lumefantrine) will be used as rescue medication in KAE609 patients meeting the treatment failure criteria (see Section 5.5.6). Any patient on KAE609 who does not need rescue medication up to Study Day 28 will be given Coartem at the end of the study (Study Day 29) and will be followed as per standard medical care.

Visits to assess safety and efficacy will be scheduled during the follow-up period as described in the assessment schedule table (Table 6-1). If malaria symptoms re-emerge outside the scheduled study visits, patients will be instructed to contact the investigator as soon as possible. For severe malaria, rescue medication according to local guidance will be used.

Frequent blood samples (see Table 6-1) for monitoring blood chemistry parameters including ALP, ALT, AST, total bilirubin (direct and indirect), creatinine phosphokinase levels, LDH, and haptoglobin. Additional samples will be collected for safety analyses at baseline and at predefined time in case of observed LFT elevations (e.g., viral hepatitis). Additional sera will be saved for possible further analyses to assess the mechanism of hepatic toxicity, if needed (e.g., miR122).

The safety of the entire study will be overseen by a primarily internal Novartis safety review committee with inclusion of at least one external hepatologist (Section 8.4).

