5.2 Treatment arms

Patients will be randomized in a 1:1 ratio between KAE609 single dose and Coartem in Cohort 1. Patients will be randomized in a 1:1:1 ratio between KAE609 single and repeated doses and Coartem in Cohort 2. Patients will be randomized in a 2:2:1 ratio between KAE609 single dose and repeated dose and Coartem in Cohort 3 and Cohort 4. Patients will be randomized in a 2:1 ratio between KAE609 single dose and Coartem in Cohort 5 and Cohort 6.

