9.7 Interim safety review

Safety laboratory data and adverse events will be monitored continuously throughout the study using data management's data review reports.

If there is no significant LFT elevations observed in a cohort at Day 15 (see [Table 3-1](#)), the next cohort with escalated KAE609 doses will start after informing the safety review committee about the findings.

If any significant LFT elevation is observed at Day 15 in any patient(s) in a cohort (see [Table 3-1](#)), a comprehensive safety data review will be performed after all the patients in the cohort have been followed up for 28 days post-treatment.

The safety review committee can pause recruitment and trigger safety review any time based on safety signals. An earlier review of the safety data by the safety review committee/Novartis in the middle of a cohort would be initiated based on occurrences of LFT elevations in the cohort as specified below:

- The number of patients meeting the primary safety endpoint in a treatment arm is at least 2 in Cohorts 1 and 2 or at least 3 in Cohorts 3, 4, 5 and 6.

Data management's data review reports will be provided to the safety review committee and the appropriate Novartis relevant internal and external people who will make decision about whether a KAE609 dosage regimen is safe and can be escalated to the higher dosage. Although the randomization data are not included in the data management system, the study drug (KAE609 QD 1 day, KAE609 QD 3 days, Coartem) and dosage taken by each patient is available in the dosage records. No formal interim safety analysis by treatment group will be performed.

In case that more comprehensive safety analyses by treatment group are needed at the end of cohort or in the middle of cohort, formal interim safety analyses of selected safety or efficacy parameters by treatment group will be provided as described in the safety review charter.

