**Table 1-1 Decision criteria for dose escalation based on LFT results with KAE 609**

LFT parameter	Baseline	Maximum post baseline value	Decision to escalate to next cohort
ALT/AST	Within ULN	< 2 times ULN (from Day 1 to Day 15 )	Escalate to next cohort after notification to safety review committee, after all the patients in the cohort have been followed for at least 14 days post treatment (study Day 15).
	> 1 to $\leq 1.5$ ULN	< 2 times baseline (from Day 1 to Day 15 )	
ALT/AST	Within ULN	$\geq 2$ to < 3 times ULN (from Day 1 to Day 15 )	Escalate to next cohort based on review of liver safety (and any other relevant data) by safety review committee, after all the patients in the
	> 1 to $\leq 1.5$ ULN	$\geq 2$ to < 3 times baseline (from Day 1 to Day 15 )	

			cohort have been followed for at least 28 days post treatment ( Study Day 29 )
ALT/AST	Any baseline value	
≥ 2 Grade (CTCAE grades) increase from baseline (at any time point during the study) in:
 
 
- 2 patients in a 10 patient cohort (Cohorts 1 and 2)
 
or
 
- 3 patients in a 20 patient cohort (Cohorts 3 and 4, 5 and 6)
 
	
Suspend recruitment and initiate review of liver safety (and any other relevant data) by safety review committee.
 
Any further progression of the study is based on the decision by the safety review committee

In consultation with the safety review committee, Novartis can suspend recruitment and trigger safety review any time based on safety signals including any potential Hy’s law case. Based on the pre-specified criteria (Table 3-1) and the review of the liver safety data by a safety review committee, the recruitment in Cohort 5 may be stopped and a lower dose of KAE609 i.e. 110 mg may be selected for Cohort 6. The study could be stopped after Cohort 5 if there is no added advantage for dosing the patients with 225 mg single dose from the perspective of future clinical development of KAE609 and its subsequent use in clinical practice.

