## 2.15 Interim safety review

Safety laboratory data and adverse events will be monitored continuously throughout the study using data management’s data review reports.

If there are no significant LFT elevations observed in a cohort at Day 15 (see [Table 1-1](#)), the next cohort with escalated KAE609 doses will start after informing the safety review committee about the findings.

If any significant LFT elevation is observed at Day 15 in any patient(s) in a cohort (see [Table 1-1](#)), a comprehensive safety data review will be performed after all the patients in the cohort have been followed up for 28 days post-treatment.

The safety review committee can pause recruitment and trigger safety review any time based on safety signals. An earlier review of the safety data by the safety review committee/Novartis in the middle of a cohort would be initiated based on occurrences of LFT elevations in the cohort as specified below:

- The number of patients meeting the primary safety endpoint in a treatment arm is at least 2 in Cohorts 1 and 2 or at least 3 in Cohorts 3, 4, 5 and 6.

Data management's data review reports will be provided to the safety review committee and the appropriate Novartis relevant internal and external people who will make decision about whether a KAE609 dosage regimen is safe and can be escalated to the higher dosage. Although the randomization data are not included in the data management system, the study drug (KAE609 QD 1 day, KAE609 QD 3 days, Coartem) and dosage taken by each patient is available in the dosage records. No formal interim safety analysis by treatment group will be performed.

In case that more comprehensive safety analyses by treatment group are needed at the end of cohort or in the middle of cohort, formal interim safety analyses of selected safety or efficacy parameters by treatment group will be provided as described in the safety review charter.

Below is the outline of the data required for the SRM review.

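### The escalation table states its suspension count per cohort where the KAE609 arm is meant, caps its review row below 3×, and is not matched by the SAP's committee categories

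*Protocol*

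**What the plan says.** Protocol Table 3-1 (Section 3.1) has three tiers for ALT/AST:

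- **Peak below 2× by Day 15** (× ULN if baseline is normal, × baseline if it is raised): escalate once the committee has been notified.
- **Peak from 2× to below 3× by Day 15:** escalate only after committee review, once all patients in the cohort have reached Day 29.
- **Rise of two or more CTCAE grades at any time:** suspend recruitment if it is seen in 2 patients (Cohorts 1 and 2) or in "3 patients in a 20 patient cohort (Cohorts 3, 4, 5 and 6".

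SAP Table 1-1 uses the same unit: "3 patients in a 20 patient cohort (Cohorts 3 and 4, 5 and 6".

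Protocol 9.7 words the mid-cohort trigger differently: "The number of patients meeting the primary safety endpoint in a treatment arm is at least 2 in Cohorts 1 and 2". For the later cohorts the threshold there is 3. SAP 2.15 agrees: "in a treatment arm is at least 2 in Cohorts 1 and 2 or at least 3 in Cohorts 3, 4, 5 and 6". Protocol 9.8.1 calculates the rule's probabilities per treatment group.

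Protocol 9.7 also has two general branches, both referring to Table 3-1 for what counts as significant. With no significant elevation at Day 15, "the next cohort with escalated KAE609 doses will start after informing the safety review committee about the findings". The other branch begins "If any significant LFT elevation is observed at Day 15 in any patient(s) in a cohort" and leads to a comprehensive review after 28 days of follow-up.

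SAP 2.8.2 defines codes 0, 1 and 2 for the committee, to be used if required, and says that they are based on Table 3-1. Code 1 is a one-grade rise if baseline is normal, or at least 2× baseline if it is raised. Protocol 9.5.2.2 specifies a count of patients at or above 2× ULN (normal baseline) or 2× baseline (raised baseline).

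**The concern.** Table 3-1 is the rule on which escalation depends, in a trial set up because of unexplained liver enzyme rises. It should be complete and unambiguous on its face. Three things fall short.

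1. **Unit.** The count is tied to a cohort size that no cohort from 2 to 6 has. Someone applying the table literally could pool arms and would then not be using the rule whose probabilities the protocol states.
2. **Cap.** The table requires review for a 2.5× peak. It has no row for a 4× peak, or for a two-grade rise below the count, although a two-grade rise is the primary endpoint.
3. **SAP derivation.** The committee display said to implement the table does not use the cut-off that separates its first two tiers when baseline is normal. The protocol's own count at that cut-off has been left out without being recorded as a change.

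**Working it through.** **Cohort and arm sizes.** Protocol 3.1 gives the early KAE609 arms as "a smaller number (N=10) of patients will be included (10 mg Single Dose (SD), 25 mg SD and 10 mg 3 Days", and later arms as 20. Protocol 5.2 gives the ratios, for example "Patients will be randomized in a 2:2:1 ratio between KAE609 single dose and repeated dose and Coartem in Cohort 3 and Cohort 4". Hence:

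- Cohort 1: 10 + 10 = 20
- Cohort 2: 10 + 10 + 10 = 30
- Cohorts 3 and 4: 20 + 20 + 10 = 50 each
- Cohorts 5 and 6: 20 + 10 = 30 each

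The sum is 20 + 30 + 50 + 50 + 30 + 30 = 210, the planned total. The figures 10 and 20 in the table are therefore KAE609 arm sizes.

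**The plan's own figures.** Protocol 9.8.1 states that the trigger probability is above 80% (n = 10) and above 90% (n = 20) at a true rate of 30% or more, and under 5% at 3% or less. Exact binomial, per arm:

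- n = 10, count 2, rate 3%: 1 − 0.97^10 − 10(0.03)(0.97^9) = 1 − 0.7374 − 0.2281 = 0.0345
- n = 20, count 3, rate 3%: 1 − 0.97^20 − 20(0.03)(0.97^19) − 190(0.03²)(0.97^18) = 1 − 0.5438 − 0.3364 − 0.0988 = 0.0210
- Rate 30%: 0.851 (n = 10) and 0.965 (n = 20)

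All the stated bounds hold with the arm as the unit.

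**Same counts applied to all KAE609 patients in a cohort, rate 3%.**

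- Cohort 2, at least 2 of 20: 1 − 0.5438 − 0.3364 = 0.1198
- Cohorts 3 and 4, at least 3 of 40: 0.1178
- Cohorts 1, 5 and 6 have one KAE609 arm, so nothing changes

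The 5% bound fails for the two-arm cohorts, and in the direction of suspending too often.

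**The tiers against Section 9.7.** For a KAE609 patient below the suspension count:

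| Peak by Day 15 | Table 3-1 alone | With Section 9.7 |
|---|---|---|
| Below 2× | Notify, then escalate | Same |
| 2× to below 3× | Review after Day 29 | Same |
| 3× or more, or a two-grade rise | No row | Review after 28 days, if regarded as significant |

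The last cell depends on the word significant, which Section 9.7 defines only by pointing back to the table that has no row for the case.

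**SAP 2.8.2 against the table.** For a raised baseline, code 1 uses 2× baseline and matches. For a normal baseline it uses one CTCAE grade, where the table uses 2× ULN. The documents do not print the CTCAE limits. If grade 1 is assumed to start just above ULN, a patient peaking between 1× and 2× ULN is coded 1 although the table puts that patient in the notify-only tier. Among the SAP outputs, 2.8.2 keeps the CTCAE shift table and Table 2-2 starts above 3× ULN. None gives the count specified in Protocol 9.5.2.2, and SAP Section 4 reports no change from the protocol.

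**The case against.** The strongest reply is that the documents already settle most of this. Sections 9.7 and 9.8.1 and SAP 2.15 name the arm or treatment group, and the table's title limits it to KAE609. A patient at 3× or more fails the first tier, so nothing in the table permits escalation on notification alone, and no sensible reader of Section 9.7 would call 2× significant and 3× not. The SAP codes are an optional display, and the committee also receives shift tables, liver abnormality categories and eDISH plots. All of this stands, and it limits the weight. It does not make the table's unit right, supply the missing row, or make code 1 follow the rule that it cites.

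Some stronger readings are tempting and are not supported:

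- **That arms often escalate without a rule.** At a 3% rate, an arm has at least one two-grade rise but stays below the count with probability 0.228 (n = 10) or 0.435 (n = 20). That shows how often a reader of the table must turn to Section 9.7. It is not the chance of escalation without review.
- **That rises first seen after Day 15 escape oversight.** Protocol 3.1, 3.6 and 9.4.4 all place peaks within about two weeks. Monitoring is continuous, recruitment can be suspended at any time, marked rises require repeat tests and SAE reporting, and Section 8.4 refers to regular reviews under a charter that is not available here. The documents give no share of late rises, so no probability can be attached. A separate late trigger would be a design preference.
- **That the SAP never states the 2× cut-off.** SAP Table 1-1 prints it; only the output tables lack it. The criteria mentioned in SAP Table 2-6 could mean Table 1-1, and the committee's output shells are not available.

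**Conclusion.** The point holds as a correction to a decision table and one derivation, and its weight is minor. The unit is wrong as written, although the intended one is clear. Misreading it would raise the trigger probability at a 3% true rate from 3.5% or 2.1% per arm to about 12% in a two-arm cohort, on the cautious side. The 3× cap leaves the table incomplete, and Section 9.7 closes the gap by implication for rises seen by Day 15. SAP code 1 departs from its stated source for a normal baseline; on the assumption that grade 1 starts just above ULN, it flags too many patients and hides none. The omission of the Protocol 9.5.2.2 count is real, and it concerns a descriptive safety summary.

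A reader might infer that the plan allows unsafe escalation or that the primary analysis is affected. Neither follows: the review and suspension safeguards apply throughout, and the primary endpoint and its analysis do not use these tiers or codes.

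**What to change.** 1. In Protocol Table 3-1 and SAP Table 1-1, state the suspension count per KAE609 treatment arm of 10 or 20 patients. The counts of 2 and 3 stay.
2. Remove the upper limit of 3× from the middle tier, so that any peak of 2× or more by Day 15, below the suspension count, goes to committee review after Day 29. This writes down what Section 9.7 implies. It also takes in a two-grade rise by Day 15 if such a rise is always at least twofold; since the grade limits are not printed, the row can name it explicitly.
3. In SAP 2.8.2, define code 1 as at least 2× ULN (normal baseline) or at least 2× baseline (raised baseline), without a two-grade rise. Restore the Protocol 9.5.2.2 count as an output, or record its removal in SAP Section 4.

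The cost is wording in two tables, one changed derivation and one descriptive count. No patients, visits, samples or enrolment pauses are added, and the primary analysis is untouched.

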3.2 Rationale for study design

This will be a multicenter, open-label, randomized, sequential, dose escalation study in adults with uncomplicated *P. falciparum* malaria.

The objective of this dose escalation study design is to characterize hepatic safety aspects of single- and multiple ascending doses of KAE609 and determine the maximum tolerated dose of the investigational drug KAE609 in malaria patients.

Dose escalation sequential design of the study is the standard design for evaluating safety and tolerability of a new chemical entity in the early phase (Phase I and II) of clinical development. Single doses up to 75 mg and repeated dosing up to 30 mg (3 day QD) have been evaluated in patients without any significant hepatic tolerability issue with the exception of LFT elevations observed in human challenge study at 10 mg single dose and 75 mg single dose in proof of concept (PoC) extension study. Single as well as repeated doses will be evaluated in this study since knowledge about safety profile of both schedules is important to inform further development of the dosing strategy with the best benefit risk profile. Single dosing is a necessary step prior to repeat dosing and allows the detection and management of adverse events (AE) which may be more severe with repeated dosing. Hence, to characterize the safety profile of the entire dose range of KAE609, patients will be first dosed with a single dose of lowest strength i.e., 10 mg and be escalated in a stepwise manner.

Coartem will be used as reference group to help distinguish if the hepatic events and other adverse events observed in the study are exclusive to KAE609 or resulting from the disease (*P. falciparum* malaria) itself.

Coartem will be dosed in the fed state. Furthermore, KAE609 will be dosed (irrespective of fed state) as single dose or QD for 3 days whereas Coartem will be dosed as twice a day (BID) for 3 days. Considering the differences in food requirement and differential frequency of administration for both the drugs, achieving blinding for patients and investigators is not feasible. The risk of bias arising out of the open-label design is minimized due to the fact that objective endpoints have been chosen for the study.

The patient population will be described in more detail in the [Section 4](#) below

